N-of-few Study of Pain Perception (NOF)

NCT04664400

Study protocol – approved 04/02/2021

SOCIAL, BEHAVIORAL, and NON-CLINICAL RESEARCH PLAN

CPHS template v. 04172017

Please complete: CPHS#00032171PI: [name] (PI); [name] (post-doc)

Important Note: The CPHS Department (Chair & Scientific) Review Form is required with this application. Find the form in the RAPPORT Library or on the CPHS Website.

- Respond to each item, even if to indicate N/A or not applicable
- Attach and/or upload this form as your 'Investigator Protocol' in Rapport
- If you are completing this form on a Mac, indicate your answer to any checkboxes by bolding or highlighting, or by deleting any incorrect options.

1. Introduction and Background

Pain perception has been shown to depend on many factors beside the sensory properties of the stimuli (e.g. temperature for heat stimuli), including expectations, past experience, social cues and context ^{1–8}. Previous studies have shown, for example, that pairing cues with low/high painful heat stimuli through symbolic learning (without actual pain delivery) induces higher pain expectations and pain responses (pain ratings, skin conductance responses (SCRs) and brain responses) to identical heat stimuli when it is preceded by the high versus the low cue in a subsequent test task ^{4,9}. Interestingly, this effect persisted although the cues were never predictive of pain intensity. The effect was shown to be driven by two processes: (1) a positive loop of modulated perception: pain responses are affected by cue-based expectations, which are in turn affected by previous pain responses; and (2) learning is affected by a confirmation bias, where expectations updating is stronger when the difference between the expected stimulus and the sensory information (the prediction error) matches the expected direction (i.e. when pain is higher than expected following high pain cues or lower than expected following low pain cues) ⁴. Other studies have shown that cues that are paired with different heat intensities via classical conditioning, with no or minimal instructions, affect pain responses and also generalize to perceptually and conceptually similar cues, but only for some of the participants and via the modification of explicit expectations ^{5,6}.

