These studies demonstrate that, perhaps surprisingly, symbolic conditioning or suggestion-based manipulations affect pain perception more than experience-based conditioning. There are, however, a few properties that are common to the above described studies. In these previous studies: (1) there was only one session with a limited number of trials (for example, 10 test trials without extinction for the symbolic conditioned cues in Jepma et al., 2018 ⁴ and 24 conditioning trials per cue, out of which only half were in fact low/high in accordance with the preceding cue rather than an identical moderately intense stimulus, in Koban et al., 2016 ⁸); (2) the difference between low and high pain stimuli was somewhat ambiguous, as the stimuli were relatively short (1 second at peak temperature) and the difference between low and high intensity was 1-2°C; and (3) in some of them, conditioned cues were combined with social cues. The social cues may have interfered learning of the cue-intensity pairing ^{5,8}. Overall, it is likely that the effect of conceptual conditioning and suggestions will eventually be extinct, and that experience-based conditioning will affect pain perception of all or most participants, across many trials or sessions, or when the low/high heat stimuli are more distinctive.

Another factor that has been shown to affect pain perception is the context. For example, an identical moderate heat stimulus was perceived as less painful (based on pain reports, SCRs and brain responses) when it was the better ("relative relief context", the other alternative was high heat) compared to the worst ("control context", the other alternative was low heat) option ^{7,10}. However, the results of these studies can be explained by the positive/negative affective response evoked by the visual representation of the outcome before heat onset, also presumably affecting expectations. Therefore, it is interesting to test whether the

counterfactual option affects pain perception when the outcome is not presented beforehand, and also when the alternatives are qualitatively, not just quantitatively, different.

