Furthermore, since pain reports are not an objective measure of pain, it is important to test how additional measures are affected by the processes described above. While the above described studies have tested SCRs and brain responses, we plan to further test how the factors described above influence additional pain-related measures, such as facial expressions, the heat signature of the face/body (with thermal imaging) and heart rate, as well as participant's confidence in their expectations' ratings.

We plan to utilize an "N-of-few" approach, where comprehensive data are collected from a few participants across many sessions, in order to test how the effects of symbolic learning, conditioning and context unfold over time. In addition, since we recently established our lab at Dartmouth and purchased new equipment, we plan to test the "dose response" of various measures to heat stimuli of different intensities, without cues or manipulations: pain reports, expectations, physiological responses, facial expressions and heat signature of the face/body. Finally, the "N-of-few" design is also more feasible now during the COVID-19 pandemic, to minimize the number of participants and allow the participation of members of our department (Psychological and Brain Sciences).

2. Objectives and Hypotheses

- Test the "dose response" curves of pain ratings, expectations, physiological responses (e.g. SCRs, heart rate, respiration), facial expressions and heat signature of the face/body (with thermal imaging) across heat intensities and multiple sessions. These curves will be used as baseline for the current as well as other studies in our lab with the same equipment.
- 2) Study how the effects of pure instructions or symbolic learning on expectations and pain perception, when cues are never in fact predictive of actual heat intensity, unfold over time. We hypothesize that biased perception and biased learning will support the effect as was shown before, but that it will decrease across sessions until complete extinction in our longitudinal design.

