- 3) Study how expectations and pain perception unfold over time following conditioning without suggestion. We hypothesize that by substantially increasing the number of conditioning trials and sessions, as well as using more distinctive stimuli, we will induce stronger effects for all or most participants. We further hypothesize that such pure experience-based conditioning will strongly affect physiological responses, but heat evoked responses may decrease due to physiological preparatory or stress responses evoked by the cues.
- 4) Study how counterfactual monetary and pain-related outcomes affect pain responses. We hypothesize that heat stimuli will be more painful when the alternative option is better (e.g. lower heat or gaining money) compared to when the alternative option is worse (e.g. higher heat or losing money).

3. Study Design

Describe all study procedures, materials, and methods of data collection:

[figure not shown]
General design and procedures

This study is an "N-of-few" study, with a few participants completing 10 sessions each. The study includes four main components:

- 1) "Dose response".
- 2) Videos affective ratings task.
- 3) Cue-pain conditioning.
- 4) Counterfactual task.

The first part (~15 minutes) of each session will be dedicated to the "dose response" component. The second part of each session (~15 minutes) will be dedicated to the video watching task. The third part of each session (~30 minutes) will be dedicated to the cue-pain conditioning component. Finally, the last part of sessions 7-10 (~20 minutes) will be dedicated to the counterfactual task. The first session will also include a first part of consent, general instructions and demonstrations, to familiarize participants with the

experimental procedures and ensure that the heat stimuli we deliver to them during the experiment are tolerable. The four components will be described in detail below.

Across components 1, 3 and 4, participants will experience thermal pain stimuli delivered to different sites on their arms / legs. Pain stimuli will be delivered using a contact thermode (Medoc, Inc.; see details about the system below) that is placed against the skin. During and / or following stimuli, participants will be asked to rate how painful, intense and/or unpleasant was the stimulus they perceived. Prior to onset of some of the stimuli, participants will be asked to rate the expected intensity and their confidence in these expectations.

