For each participant, each cue will be paired with a distribution of low or a distribution of high heat stimuli in one of three ways: pure instructions, symbolic learning and/or experience-based conditioning. We will then test how each of these pairing methods affect anticipatory and pain responses across time following the different cues. We will also include an additional neutral cue that will not be paired with any intensity, to serve as a baseline condition. The "cue-pain conditioning" component will include the four following tasks:

[figure not shown]
 Symbolic learning: This task will be similar to previous studies in our lab ^{4,9}. Low/high cues will be paired with pictures of thermometers showing low/high temperatures, respectively, without pain delivery. These cues will not be predictive of actual intensity in the following tasks that will include heat stimuli.

- 2) *Conditioning*: Low/high cues will be paired with heat stimuli taken from low/high intensity distributions, respectively, without suggestion. These cues will be predictive of actual intensity in the conditioning task, but not in the test task (see below).
- 3) *Test*: All cues will be presented in this task in a pseudo-random order and will be proceeded by heat stimuli with moderate intensity. This will allow us to compare the effect of the different cues on expectations and pain responses evoked by the same moderate stimuli. More than one moderate temperature will be used in the test task, to ensure that heat intensity affects pain responses, and pain reports are not driven by demand characteristic.
- 4) *Cues recognition*: In this task, all cues will be randomly presented one by one and participants will be asked to rate how hot they expect the stimulus paired with this cue to be. This task will be used to test explicit learning, in addition to the expectation ratings during the test task.

In the pure instructions condition, participants will be instructed for each cue whether it is paired with low or with high heat stimuli, without further conditioning. These cues will not be predictive of actual intensity in the following tasks.

In order to control for order effects between the symbolic learning and conditioning tasks, their order will be counter-balanced across sessions and participants (see below).

The structure of the tasks across the 10 sessions will be as follow (the order of the symbolic learning and conditioning tasks will change between participants):

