The first session will include all tasks: first the conditioning tasks, then the test task and finally the cues recognition task. Sessions 2-6 will begin and end with the cues recognition task (to test for explicit learning between and within sessions), and include the learning tasks (symbolic learning and conditioning) as well as a test task. These sessions will be used to establish the pairing of cues and heat intensity, and to test the learning process. Sessions 7-10 will only include the cues recognition and test tasks, in order to test how the effects of previous learning unfold over time without further learning.

"Counterfactual"

In the counterfactual task, on each trial participants will be presented with one of the following binary alternatives:

- Low vs. moderate heat stimulus
- High vs. moderate heat stimulus
- Gaining money vs. moderate heat stimulus
- Losing money vs. moderate heat stimulus

Participants will be told that on each trial one of the two alternatives will be randomly chosen (50% chance each). Then, one of the alternatives will be pseudo-randomly chosen by the computer, and participants will either experience a low/moderate/high heat stimulus or will gain/lose money (+/- 3\$-6\$). Participants will not be asked to choose and will have no control on the outcome, but rather will be presented with the alternative option that was not chosen. This will allow us to test the pain responses to the same moderate

stimulus depending on the counterfactual- whether it was the better or the worse option, and whether the alternative option was a different intensity of heat or a monetary outcome.

To avoid a situation where participants randomly lose money during the experiment with no control from their side, we will make sure that while they may lose money in a given session (out of their compensation for this specific session), in total, across the four sessions with the counterfactual task, their gains and losses will sum to \$0 or more.

Additional COVID-19-related procedures

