The behavioral research procedures as described in the research plan will be carried out in the laboratory utilizing the 2020 re-opening plans and COVID-19 protection protocols as long as these are in place. We will strictly follow Dartmouth College's policies. We hope to enroll 10 voluntary participants, from the college / surrounding community or from subpopulations, as allowed by COVID-19-related policies at the time of recruitment and participation.. Equipment utilized for these behavioral interventions include, as described above, Thermode systems, the BioPac Acquisition System, cameras (GoPros and a Thermal camera) and computers. Cleaning procedures for these devices are in place as part of the lab's approved reopening plan and will be strictly followed (see Attachment2- CANlab phase 2A lab reopening worksheet_9.2.2020]).

4. Analysis

Describe any qualitative tests and measures as well as quantitative methods:

Data will be analyzed via univariate and multivariate regression models as well as statistical learning-based classification techniques and Bayesian analyses. All data will be processed, analyzed and visualized using a combination of Excel, R, JAGS, Python, Matlab and similar software.

5. Study Progress Monitoring

Note: appropriate monitoring may include periodic assessment of the following:

- data quality
- timelines
- recruitment and enrollment

Provide a description of the methods which will be used to determine the progress of the study, including periodic assessments of data quality, timelines, recruitment, and enrollment as appropriate:

Study progress will be periodically monitored. We will test the timeline and protocol of the study before recruiting participants. Following the collection of data from the first participants and sessions, we will visually observe the data and run preliminary analyses to ensure data quality. Those steps will allow us to make informed decisions about potential study alterations. Since we plan to collect extensive data from each participant, and taking into account the challenges and restrictions of participants' recruiting during these unpredictable times, we may change the planned compensation or the number and duration of sessions and amend this protocol accordingly. Those aspects will be monitored continuously by the research team.

6. Risks & Benefits

Note: Risks may be physical, psychological, social, legal, economic, to reputation, or others.

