N-of-few Study of Pain Perception (NOF)

NCT04664400

Statistical Analysis Plan

8/3/22

Statistical analysis plan

Our main statistical analysis will be focused on participants' pain ratings following high vs. low cues for each of the conditions (symbolic learning, conditioning, and instructions only). For each condition, we will report the mean and standard deviation across participants test for significant differences in pain ratings following low vs. high cues with paired t tests, using statistical threshold of alpha = 0.05.

For the counterfactual task, we will compare ratings of the same pain stimulus when it is the better vs. the worst alternative, reporting the mean and SD across participants for this difference, and testing for significance with a paired t test.

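### For the conditioning cues, the SAP's group mean, SD and paired t test do not by themselves show whether all or most participants have an effect, as objective 3 hypothesises

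*SAP*

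**What the plan says.** **The hypothesis.** Objective 3 (Protocol section 2) states, of conditioning without suggestion, that "we will induce stronger effects for all or most participants". Protocol section 1 makes the same prediction for pain perception: "experience-based conditioning will affect pain perception of all or most participants, across many trials or sessions". It sets this against earlier studies, where conditioned cues had effects "but only for some of the participants and via the modification of explicit expectations".

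**The planned analysis.** The SAP makes pain ratings after high and low cues its main analysis, separately for symbolic learning, conditioning and instructions only. For each it says "we will report the mean and standard deviation across participants" and plans a paired t test at alpha 0.05. It specifies no individual estimate, interval, plot or count. Protocol section 4 is broad: "Data will be analyzed via univariate and multivariate regression models as well as statistical learning-based classification techniques and Bayesian analyses". It ties none of these methods to effects in individual participants.

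**The data available.** The cue-pain conditioning part of Protocol section 3 places the test task in all ten sessions. Learning tasks run in sessions 1 to 6; after that, "Sessions 7-10 will only include the cues recognition and test tasks". The test heat is not a single level: "More than one moderate temperature will be used in the test task". The number of participants is put at 5 to 10 (section 9a), with 10 hoped for (section 3, COVID-19 procedures).

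**The concern.** All or most is a statement about how many individuals show an effect. A mean, an SD and a p-value are statements about the average and its spread. The protocol's case for the study is partly that earlier conditioning reached only some people, so the difference between some and most is part of what it sets out to learn. If the SAP is followed exactly, a significant result could be read as support for that part of objective 3 when it supports only a non-zero mean. A non-significant result could be read as a failure of conditioning when every participant shifted in the same direction. If individual effects are examined later without a plan, the definition of an effect would be chosen after the ratings had been seen.

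**Working it through.** **Inputs.** N = 5 to 10 (Protocol 9a) and alpha = 0.05 (SAP). The SAP does not state sidedness; two-sided is assumed. The documents give no effect size, SD, trial count or power figure, so there is no planned figure to reproduce and all rating values below are illustrative. The SD is taken as that of the within-participant difference, the reading most favourable to the plan.

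**1. Same outputs, different answers (N = 10).** For differences d, t = mean / (SD/√N).

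- Five at 0, five at 20: mean = 100/10 = 10; sum of squares about the mean = 10 × 10² = 1000.
- Eight at 5, two at 30: mean = (40 + 60)/10 = 10; sum of squares = 8 × 5² + 2 × 20² = 200 + 800 = 1000.

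Both give SD = √(1000/9) = 10.54, t = 10/(10.54/√10) = 3.00 and p = 0.015. The first has 5 of 10 positive, the second 10 of 10.

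The reverse also occurs: nine at 1 and one at 30 are all positive, yet mean 3.9, SD 9.17, t = 1.34, p = 0.21.

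**2. What a significant result does force.** If k of N differences are positive and the rest are zero or below, then (Σd)² ≤ kΣd², so the largest possible t is √[k(N − 1)/(N − k)].

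| N | critical t | largest t, k = 3 | largest t, k = 4 | 4/N |
|---|---|---|---|---|
| 5 | 2.776 | 2.449 | 4.000 | 80% |
| 6 | 2.571 | 2.236 | 3.162 | 67% |
| 7 | 2.447 | 2.121 | 2.828 | 57% |
| 8 | 2.365 | 2.049 | 2.646 | 50% |
| 9 | 2.306 | 2.000 | 2.530 | 44% |
| 10 | 2.262 | 1.964 | 2.449 | 40% |

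Three positives never suffice and four can. Significance in the expected direction therefore guarantees a majority of positive observed differences at N = 5 to 7, but not at N = 8 to 10.

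**3. How often this could arise.** Simulated t tests with an assumed person-level error SD of 5 and responder effects of 5, 10 and 20 points are significant this often:

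| True responders | 5 | 10 | 20 |
|---|---|---|---|
| 5 of 10 | 22% | 48% | 81% |
| 4 of 10 | 15% | 29% | 47% |
| 4 of 8 | 17% | 34% | 54% |
| 2 of 5 | 7% | 9% | 4% |
| 10 of 10 | 80% | 100% | 100% |

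Half of ten responding by 20 and all ten responding by 5 give almost the same chance of significance (81% and 80%). With 2 of 5 responding, significance is rare.

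**4. Why individual intervals must allow for correlation.** A plain t interval on six session values, with no true effect, excludes zero in one given direction 2.5% of the time if sessions are independent. At lag-1 correlation 0.3 this is 6.2%, and at 0.5 it is 11.0%.

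**5. Why a count of intervals cannot settle the matter.** Suppose all ten participants have a true effect, each estimated with standard error 5 from ten independent sessions (9 degrees of freedom). The chance that one interval excludes zero is 0.144, 0.431 or 0.944 for effects of 5, 10 or 20. The binomial chance that at least 9 of 10 do so is 0.00002%, 0.3% or 89%.

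Estimates from sessions 1 to 6 alone are less precise: with the same session-level SD (5 × √10 = 15.8) the standard error is 15.8/√6 = 6.5. Under one candidate model, detection at an effect of 20 was 0.752 with no correlation and 0.444 at correlation 0.5. The chance of at least 9 of 10 is then 10 × 0.752⁹ × 0.248 + 0.752¹⁰ = 25%, or 0.4% by the same formula with 0.444.

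**The case against.** The strongest reply has three parts.

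- **The outputs are not silent.** At N = 5 to 7 a significant test already requires most observed differences to be positive. This stands, and it limits the point. A positive observed difference is still not a demonstrated individual effect, since noise alone makes about half of them positive.
- **Nothing is excluded.** The SAP describes its main analysis, and Protocol section 4 allows regression and Bayesian work. This also stands: individual-level analysis is unplanned, not ruled out. A list of method families does not, however, say which estimate would answer objective 3.
- **All or most is one phrase in a hypothesis about stronger effects.** No document makes a responder share an endpoint. That argues for a modest addition, not a new primary analysis.

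A reader might infer that the paired t test is wrong. It is not: it remains a suitable test of the mean effect. A reader might also extend the point to all three cue conditions. The documents do not support that. For instructions and symbolic learning, objective 2 predicts that the effect "it will decrease across sessions until complete extinction in our longitudinal design", which concerns time and not a share of participants. Nor would a responder count prove the hypothesis at this sample size, as step 5 of the working shows.

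**Conclusion.** The concern holds in a limited form. For the conditioning cues, the planned mean, SD and t test do not by themselves show whether all or most participants have an effect; identical outputs fit 5 of 10 and 10 of 10 positive differences. The gap matters most near N = 8 to 10, where significance guarantees only 40 to 50% positive observed differences, and less at N = 5 to 7. To say that the outputs carry no information about individuals would be too strong.

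The identity in step 1 and the bound in step 2 are arithmetic and need only the two-sided 5% level. The rates in steps 3 to 5 rest on assumed effects, SDs and correlations and show the range, not the likely value. This is a cheap improvement to the SAP, not a flaw in its main test.

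**What to change.** Keep the paired t test. Add one paragraph to the SAP, for the conditioning cues only:

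1. For each participant, compute the high-minus-low difference in test-task pain rating within each moderate temperature, then average over temperatures.
2. Display every participant's estimate with a 95% interval that allows for correlation between sessions. The model form is left to the study statistician.
3. Name in advance one estimate per participant as the one that addresses all or most, for example sessions 1 to 6, while learning continues. Show sessions 7 to 10 as secondary. State the hypothesised direction.
4. Report, as description, how many estimates lie in that direction and how many intervals exclude zero in it. State that at N = 5 to 10 these counts do not establish a population share, and that a low count of intervals excluding zero is not evidence against the hypothesis.

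**Cost.** One extra analysis, with no new data, participants or protocol change. Individual intervals may be wide. If the ratings have already been analysed, the addition must be labelled post hoc.

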- causing distress in interviews of a sensitive nature

Describe potential events and provide a plan of action:

Although we do not anticipate adverse events, we will follow reporting standards. In any case of thermodes malfunction/burn, we will stop the study and assess potential for harm to future participants. As this is a known, however very rare risk, we do not consider it as an adverse event under formal definition. Nonetheless, we will inform IRB on any such event and will investigate the incident to make sure all safety procedures are strictly followed. If necessary, we will change the protocol of the study to prevent future such incidents.

An experimenter will always be present a few feet away from the testing room in which the experiment will take place. In addition, Dick's House (on campus health services) is across the parking lot from Moore hall. Participants will be sent there should they report any symptoms of physical or mental discomfort. Any psychological, social or medical services required will be available through Dick's House and/or referral to Dartmouth Hitchcock Medical Center.

8. Deception

Does any part of this study involve deception or withholding of information from participants?

 $\boxtimes \underline{Yes}$ \Box No

If Yes, provide an explanation which addresses the following:

- A description of the deception being used
- Why the deception is necessary
- A plan for debriefing, or providing subjects with the pertinent information after participation

In the some of the tasks, we will lead participants to be believe that a cue is predictive of lower or higher heat intensities, where in fact some of the cues will not be predictive of actual heat intensities. This minimal deception is critical to test the effect of different types of suggestions/conditioning on pain perception, because the management of participants' expectations and beliefs is a one of the main focuses of the study. Participants will be debriefed about this procedure and the intended purpose of the study upon the study's conclusion (see debrief form).

9. Equitable Participant Selection

- a. Estimated number of participants at Dartmouth CPHS reviewed sites:
 - 5-10

b. Provide a justification of the proposed sample size

As described above, this study is designed as a "N-of-few" experiment to study effects on pain perception over time. This design is also in line with the current guidelines and required precautions

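### For the cue conditions the SAP specifies only a high-versus-low paired t test with no session or phase term, so neither document specifies a test of objective 2's decline to extinction or an analysis of objective 3's time course

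*SAP*

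**What the plan says.** **SAP.** The main analysis concerns pain ratings after high and low cues in three conditions: symbolic learning, conditioning and instructions only. For each, the plan gives a mean and SD across participants and will "test for significant differences in pain ratings following low vs. high cues with paired t tests, using statistical threshold of alpha = 0.05". The only other analysis is a paired t test for the counterfactual task, which serves a different objective.

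**Protocol, section 2.** Objective 2 concerns instructions and symbolic learning. It predicts of the effect that "it will decrease across sessions until complete extinction in our longitudinal design". Objective 3 is to "Study how expectations and pain perception unfold over time following conditioning without suggestion". Its time course is posed as a question; its hypotheses concern the strength of the effect and physiological responses.

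**Protocol, section 3 (cue-pain conditioning).** The text states an intention to test how each pairing method affects responses as time passes. Session 1 includes all tasks. Sessions 2-6 "include the learning tasks (symbolic learning and conditioning) as well as a test task". Sessions 7-10 drop the learning tasks, "in order to test how the effects of previous learning unfold over time without further learning".

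**Design rationale.** Section 1 adopts the N-of-few approach "in order to test how the effects of symbolic learning, conditioning and context unfold over time". Section 9b justifies the sample size (5-10 in section 9a) by describing an N-of-few "experiment to study effects on pain perception over time". Both sections also cite COVID-19.

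**Protocol, section 4.** "Data will be analyzed via univariate and multivariate regression models as well as statistical learning-based classification techniques and Bayesian analyses". No outcome, predictor or time term is attached to any of these methods.

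**The concern.** The design puts its effort into repeated sessions, with a learning phase and a later phase without learning, and objective 2 makes a directional prediction about change between sessions. The only specified cue analysis compares high with low cues and has no place for session. If it is followed as written, the average cue effect is tested and the longitudinal hypothesis is not.

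Three things are at stake. Any statement about decline or persistence would rest on a model chosen later. The size of the planned contrast depends on an unstated choice of sessions. And, with no criterion for extinction, a non-significant difference in sessions 7-10 could be reported as the predicted extinction, although with 5-10 participants that is weak evidence.

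**Working it through.** The documents give no effect size, SD or power, so there is no figure of theirs to reproduce. Inputs from the documents: ten sessions, learning tasks through session 6, none in sessions 7-10, N = 5 to 10, alpha 0.05. Assumed: a two-sided test (the SAP does not say), equal session weights, and illustrative profiles on an arbitrary rating scale.

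**1. What an averaged contrast can distinguish.** Let d(s) be the true high-minus-low difference in session s. The averaged contrast has expected value Σd(s)/10. The linear profiles are 10(10−s)/9 for the decline and 10(s−1)/9 for the rise. The ten-session slope is Σ(s−5.5)d(s)/82.5.

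| Profile | Mean, all ten | Mean, 1-6 | Mean, 7-10 | Change, 1-6 to 7-10 | Ten-session slope |
|---|---|---|---|---|---|
| Flat 5 | 5.0 | 5.0 | 5.0 | 0 | 0 |
| Decline 10 to 0 | 5.0 | 7.22 | 1.67 | −5.56 | −1.11 |
| Rise 0 to 10 | 5.0 | 2.78 | 8.33 | +5.56 | +1.11 |
| 10 in sessions 1-6, then 0 | 6.0 | 10 | 0 | −10 | −1.45 |

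The first three rows have the same average, so the averaged contrast cannot tell them apart in expectation. The second row shows how much the choice of sessions matters: 7.22, 5.0 or 1.67. The last row shows why slopes fitted separately within each phase should not be the main analysis: both would be exactly zero although the effect has vanished. The change between phases detects it.

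**2. Late non-significance as evidence of extinction.** Take as the unit the SD across participants of their mean difference in sessions 7-10. Suppose a true effect of 0.5 SD remains. The t statistic is non-central with parameter 0.5√N.
- N=10: parameter 1.58, critical value 2.262, power 0.293, so non-significant 71% of the time.
- N=5: parameter 1.12, critical value 2.776, power 0.141, so non-significant 86% of the time.

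**3. Precision of the late mean.** The 90% interval half-width, with the sample SD as unit, is t(0.95, N−1)/√N.
- N=10: 1.833/3.162 = 0.58 SD.
- N=5: 2.132/2.236 = 0.95 SD.

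If the true late effect is zero, the chance that the 90% interval lies inside ±1.0 SD is 0.795 at N=10 (simulation). At N=5 it takes ±1.6 SD to reach 0.80.

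**4. Power of the phase change (illustration).** Assume each participant's effect declines linearly to zero, with a participant's ten-session mean distributed with mean 5 and SD 8, and a session-level SD of 8. The mean change is 5.56 in size. Its between-person SD is 1.111 × 8 = 8.89, and its session noise is 8√(1/6 + 1/4) = 5.16. The total SD is √(8.89² + 5.16²) = 10.28, and the standardised change is 5.56/10.28 = 0.54. Non-central t power is about 0.33 at N=10 and 0.16 at N=5. For the ten-session slope under the same assumptions it is 0.35 and about 0.16. Neither is powerful, and the figures move with the assumed SDs.

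**The case against.** The strongest reply is that time modelling is already intended. Section 3 of the protocol says responses will be tested as time passes, section 4 names regression and Bayesian methods, and the SAP describes only the main analysis. This stands against a stronger reading that a reader might infer: that the investigators planned no look at the time course, or ruled it out. The documents do not support that. What remains is narrower: the aim is stated, but no outcome, term, contrast or criterion is attached to it. A list of method families does not say what would count as decline or extinction.

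A reader might also infer that the paired t test is wrong. It is not. It is a valid test of the average cue effect over whichever sessions are used.

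A third point is that a time-course test at N = 5 to 10 will be weak. That stands too, and it limits what the addition can show. It does not make the average contrast an answer to a question about change. It is also a reason to keep the addition small: several slopes per condition, each tested, would add comparisons without adding information.

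Finally, the documents do not say whether the instructions are given once or repeated in sessions 2-6. No analysis should presume that the instructions-only condition has no change of phase, so the same estimate should be used for all three conditions.

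**Conclusion.** The concern holds in this form: for the cue conditions the SAP specifies a high-versus-low contrast without a session or phase term and without saying which sessions enter, and neither document specifies a test of objective 2's predicted decline to extinction or an analysis of objective 3's time course.

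The main result is arithmetic and needs no assumed variance: three quite different time courses share an average of 5.0, and one decline yields 7.22, 5.0 or 1.67 according to the sessions chosen. It does rest on equal session weights and on ratings being averaged over sessions, which the SAP does not state. The 71% and 86% assume a two-sided test and a residual effect of 0.5 SD. The power of about 0.33 and 0.16 rests on assumed SDs and is illustrative only.

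This is a cheap improvement, not a flaw that invalidates the planned test.

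**What to change.** 1. Keep the paired t test as the average contrast, and state which sessions enter it and how they are combined.
2. Add one named time-course estimate, the same for all three cue conditions: each participant's change in the high-minus-low pain rating difference from sessions 1-6 to sessions 7-10, with a 95% interval. Test it for instructions and symbolic learning (objective 2). Report it descriptively for conditioning (objective 3). An equivalent cue-by-phase or cue-by-session term in a mixed model would serve as well. Show session-by-session effects and the ten-session slope as supportive; slopes within each phase are descriptive only.
3. Report the mean cue effect in sessions 7-10 with its interval, and state that a non-significant late difference is not extinction. Claim extinction only if an effect was shown in the earlier sessions and the late 90% interval lies inside a range fixed before the analysis. Otherwise say that extinction was not shown.
4. State whether data had been examined before these additions. The SAP is dated after protocol approval, and section 5 of the protocol foresees preliminary analyses of early data for quality. If data had been examined, label the additions post hoc.

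The cost is SAP wording and modest extra analysis, with no new data. The investigators must choose and defend an equivalence range. With late 90% half-widths of 0.58 SD (N=10) or 0.95 SD (N=5), extinction will often not be demonstrable, and the report should be ready to say so.
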